1. SYNOPSIS

Name of Company:Name of Product:Type of Study:KeraNetics, LLCKeraStat® CreamClinical Proof of Concept

Title of Study: Pilot Study: KeraStat® Cream for Radiation Dermatitis

Investigator(s): [name], PhD; [name], PhD

Study Period: Estimated screening expected to start March 2018; Expected completion September 2018

Phase of Development: Design & Development (Phase 3 of Design Control)

Objective(s):

Primary:

- To assess feasibility (compliance of use)
- Collect data for designing a larger future trial evaluating KeraStat Cream

Secondary:

- To assess the safety and tolerability of KeraStat Cream in subjects at risk of radiation dermatitis
- To assess the effectiveness of KeraStat Cream compared to standard of care to manage the symptoms of radiation dermatitis in subjects being treated with radiation therapy
- To estimate amount of KeraStat Cream used per patient and coverage on skin

Methodology: This is a randomized, open label study.

Number of Subjects:

Sufficient subjects will be screened and enrolled such that 24 total subjects, 12 subjects per treatment group, will complete the study through the Follow-Up Visit. With 12 participants in each treatment group, we will be able to calculate a 95% confidence interval around the compliance rate in each group with a maximum margin of error of 0.283. Comparisons between groups for effectiveness will have 80 percent power to detect a difference of 1.2 standard deviations. Results of the current study are intended to provide descriptive endpoint data to inform the design of a future clinical evaluation of product effectiveness.

Study Overview:

Study Periods:

The length of study participation for a subject is about 8-12 weeks, depending on the length of radiation treatment. The study will extend 4-6 weeks beyond the end of radiation therapy. The study will begin with a Screening Visit during treatment planning followed by weekly assessments during radiation therapy, and a follow up visit 4-6 weeks after completion of therapy. There is a total of 5-7 visits.

Study Assessments:

At the Screening/Baseline Visit (Visit 1, Week 0), following informed consent, initial eligibility will be verified per the inclusion/exclusion criteria and demographics and brief medical history will be collected. Subjects will be randomized to receive standard of care or KeraStat Cream. A physical exam and photograph of the area to be irradiated will be obtained, and subjects will complete the Dermatology Life Quality Index.

During the course of radiation therapy (4-6 weeks) and for the duration of the post RT treatment period (4-week follow up), subjects will complete a daily diary detailing symptoms and treatment details. Weekly from week 2 of RT until the end of treatment, study staff will assess the subject for radiation dermatitis by recording the RTOG for Radiation-Induced Acute Skin Toxicity scores and taking photographs. The same evaluation will be performed at the follow up visit after treatment. Subjects will complete the Dermatology Life Quality Index at each visit.

Inclusion Criteria:

Subjects must meet all of the following criteria:

- 1. Age ≥ 18
- 2. Female
- 3. Diagnosis of early stage (stage 0-2) breast cancer and scheduled to receive 4-6 weeks of fractionated radiation therapy as part of breast conserving therapy following lumpectomy

Exclusion Criteria:

Version: 00 03-01-2018

Effective Date:

Name of Company:Name of Product:Type of Study:KeraNetics, LLCKeraStat® CreamClinical Proof of Concept

To participate in the study, subjects must not meet any of the following criteria:

- 1. Previous radiation therapy to the area to be treated with radiation therapy
- 2. Receiving palliative radiation therapy
- 3. Low dose radiation protocol
- 4. Unhealed or infected surgical sites in the irradiation area
- 5. Patients undergoing cytotoxic chemotherapy or concurrent Herceptin as part of overall treatment plan (tamoxifen/aromatase inhibitor allowed)
- 6. Use of oral corticosteroids or topical corticosteroids in the irradiation area
- 7. Subjects with an autoimmune disease affecting the skin (e.g., scleroderma, systemic lupus erythematosus, psoriasis) are excluded. A history of other autoimmune disease that does not have direct skin involvement (e.g. rheumatoid arthritis, inflammatory bowel disease, multiple sclerosis) does not exclude participation on the study unless the subject requires active treatment with systemic steroids, immune suppression or biologic agents, or systemic chemotherapeutic agents (methotrexate or cyclophosphamide).
- 8. Skin disease in target irradiation area
- 9. Known allergy to the standard of care or any of the ingredients in KeraStat Cream

Test Product(s), Dose, and Mode of Administration:

Investigational: KeraStat® Cream should be applied topically to the irradiation area and 1cm beyond the border of the affected area twice daily. Expel the cream from the tube. Smooth the cream over the target area to cover with a thin layer; do not rub the cream in.

Control: The standard skin care product should be applied topically to the irradiation area and 1cm beyond the border of the affected area twice daily. Smooth the product over the target area to cover with a thin layer; do not rub the product in.

Duration of Treatment:

The length of study participation for a subject is about 8-12 weeks.

Concomitant Medication Restrictions:

Chemotherapy, steroids

Criteria for Evaluation:

Effectiveness Evaluation:

Primary

- Safety and tolerability will be evaluated throughout the study utilizing patient reported outcomes
- Adverse events will be recorded throughout the study.

Secondary

- Maximum severity of radiation dermatitis as assessed by the RTOG Criteria for Radiation-Induced Acute Skin Toxicity.
- Number of subjects with Grade I radiation dermatitis
- Number of subjects with Grade II radiation dermatitis
- Number of subjects with moist desquamation present
- Change from baseline in the Dermatology Life Quality Index

Statistical Methods:

Feasibility:

Feasibility will be determined based on the average number of applications per week for a participant. Participants who average at least 10 applications per week will be classified as compliant. A 95% confidence interval will be calculated for the observed compliance rate. Along with the compliance rate, the number of tubes of KeraStat Cream used and the estimated surface area (bra size used as a surrogate) to be covered for each participant will be used to evaluate the coverage.

Safety:

Version: 00 03-01-2018

Effective Date:

Name of Company:Name of Product:Type of Study:KeraNetics, LLCKeraStat® CreamClinical Proof of Concept

All subjects who are randomly assigned to a treatment and receive at least one application of KeraStat Cream or standard of care will be included in the safety and tolerability analysis. Safety will be evaluated by examining the incidence, grade, type of adverse events and changes in clinical laboratory test values, physical examination results, and vital signs measurements from the Screening Period through study completion.

Effectiveness:

Descriptive statistics will be generated to determine any trends and to support a power calculation for a large follow-up study. Tests comparing the two treatment groups will be done for all outcomes of effectiveness including, skin appearance, the Dermatology Life Quality Index score, and the RTOG skin score. Qualitative assessments of patient-reported skin condition and satisfaction with the intervention will be assessed for themes.

Version: 00

Effective Date:

03-01-2018

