6. INVESTIGATIONAL PLAN

6.1. Overall Study Design

This is a single site, between subject, open-label comparison pilot study to assess the feasibility and effectiveness of KeraStat Cream in managing RT skin toxicity. The length of study participation for a subject is 8-12 weeks depending on when a subject returns for her final follow-up evaluation. The Study Design Schematic is shown below in Figure 1 with the Acceptable Study Windows in Table 2.

Sufficient subjects will be screened such that 24 total subjects will complete the study. Patient compliance is expected to be good, so a target recruitment of 26 subjects is desired.

Once a RT patient is determined to be a candidate for inclusion in this study, they may be approached for consent to participate. A total of 26 breast cancer patients scheduled to receive RT will be recruited and consented.

RT will begin 4 to 10 weeks after surgery; the targeted volume will be the ipsilateral breast with or without regional lymph nodes. Once the patient has consented to participate in the study, their baseline pre-RT assessments can be completed during the radiation treatment-planning process.

Patients are generally treated with RT Monday through Friday, with weekends and holidays off, for approximately 4 to 6 weeks. Patients will be provided with KeraStat Skin Cream for application as often as needed but at least twice daily, morning and evening.

During the course of treatment, the patient sees the radiation oncologist weekly in clinic to review the patient's treatment course, monitor the skin's appearance after application of KeraStat Skin Cream or standard of care, and answer questions. Breaks in the treatment schedule should be avoided whenever possible, but breaks necessitated by RT skin toxicity or for other reasons will be recorded. The radiation oncologist will see each patient in follow-up 4-8 weeks after completing RT to assess the patient for RT-induced skin and other toxicities that may have occurred.

Version: 00

Effective Date: 03-01-2018

Figure 1: Study Design Schematic

Table 2: Acceptable Study Windows

Visit	Day Visit	Acceptable Visit Window
Screening (Visit 1)	Day 1	None
Baseline (Visit 1)	Day 1	None
First evaluation (Visit 2)	RT Day 8	±2 days
Second evaluation (Visit 3)	RT Day 15	±2 days
Third evaluation (Visit 4)	RT Day 22	±2 days
Fourth evaluation (Visit 5)	RT Day 29	±2 days
Fifth evaluation (Visit 6)	RT Day 36	±2 days
Final evaluation (Visit 7)	Post RT Day 30	±14 days

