6.4. Treatment Assignment

All subjects will be randomized to receive one of two test agents: KeraStat Cream or standard of care (physician-directed care).

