6.5. Study Procedures

6.5.1. Visit 1

After obtaining consent, ensuring the subject meets study inclusion/exclusion criteria, and randomizing the subject, study personnel will photograph the site to be irradiated. Study personnel will collect vital signs. Subjects will complete the Dermatology Life Quality Index. Study personnel will provide KeraStat Cream to subjects randomized to receive KeraStat Cream. Subjects randomized to standard of care will follow the instructions of their radiation oncologist. Study personnel will provide subjects with a daily diary form where subjects will note symptoms or treatment details of concern.

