9.5. Administration

KeraStat Skin Cream has been shown to moisturize the skin and reduce dryness, redness, and the appearance of inflammation. It should be applied as needed but at least twice daily.

In this study, patients will apply the cream at least twice-daily during the radiation treatments, 7 days per week.

Version: 00

Effective Date:

03-01-2018

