12. STATISTICS

12.1. Description of Statistical Methods

Descriptive statistics will calculated and used to inform additional device development and to inform a power calculation for a follow on study, if required. The completion rate will be used as a measure of feasibility, with participants with an average of 10 or more applications per week being classified as compliant. A 95% confidence interval will be calculated around the estimate of compliance. After summary statistics are calculated by group, a t-test will be used to compare the two treatment groups for the effectiveness outcomes of DLQI score and RTOG score. A Fisher's exact test will be used to compare skin appearance issues between the groups. The counts for each type of adverse event will be summarized by grade and treatment group. For the KeraStat treatment group, the mean coverage will be calculated per square centimeter.

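### The control arm has two different regimens (twice-daily product, or physician-directed care), yet one cut-off of 10 applications a week scores compliance in both arms, over a period the plan does not state

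*Combined protocol and SAP*

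**What the plan says.** **Control arm.** The synopsis, under Test Product(s), Dose, and Mode of Administration, gives a set frequency: "The standard skin care product should be applied topically to the irradiation area and 1cm beyond the border of the affected area twice daily". Section 6.4 equates the same arm with care chosen by the physician ("standard of care (physician-directed care"). Sections 6.5.1 and 6.5.2 both state: "Subjects randomized to standard of care will follow the instructions of their radiation oncologist". No control product is named.

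**KeraStat arm.** The synopsis says twice daily. Section 6.1 supplies the cream "for application as often as needed but at least twice daily, morning and evening". Section 9.5 adds a period: "patients will apply the cream at least twice-daily during the radiation treatments, 7 days per week". The synopsis, under Study Assessments, has subjects keep a diary that includes treatment details during RT and also "for the duration of the post RT treatment period (4-week follow up" (the bracket closes there). Its Duration of Treatment entry gives only the 8 to 12 weeks of participation.

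**Compliance.** Section 11.1 defines feasibility through weekly application counts but names no averaging period. The synopsis and section 12.1 class a participant as compliant at a mean of 10 or more per week, and 12.1 adds: "A 95% confidence interval will be calculated around the estimate of compliance". The synopsis (Number of Subjects) and section 12.2 plan that interval for each group, so the cut-off applies to control as well.

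**Effectiveness.** Section 12.1 states that "a t-test will be used to compare the two treatment groups for the effectiveness outcomes of DLQI score and RTOG score".

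**The concern.** Feasibility, meaning compliance of use, is a primary objective. A compliance rate has meaning only against an assigned regimen and over a stated period. The two descriptions of control imply different comparators, and only the twice-daily one has a frequency against which 10 per week can be read. Under the other, a control subject can do exactly what her radiation oncologist says and still be counted as non-compliant, or fall well short of her instructions and be counted as compliant.

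Two further things depend on the wording. The first is what the effectiveness comparison estimates: KeraStat against a fixed twice-daily product, or against whatever each physician advised. A future trial planned from these data needs to know which. The second is the denominator of the weekly average. Because section 11.4 builds coverage partly from the compliance rate, that denominator carries into the coverage estimate too.

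**Working it through.** **1. The plan's own figures.**
- Interval half-width at n = 12 and p = 0.5: 1.96 × √(0.25/12) = 0.2829, against 0.283 stated in section 12.2.
- Power of a two-sample t-test with 12 per arm and a difference of 1.2 SD: with two-sided alpha 0.05 (assumed, since none is stated), the noncentral t gives 0.802, against 80% stated.

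Both reproduce. Neither depends on which regimen text is followed.

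**2. Does one cut-off fit the control arm?** Under the synopsis regimen the full weekly count is 2 × 7 = 14, and the cut-off is 10/14 = 71% of it. Under sections 6.4 and 6.5 no frequency is given, so the instructions below are assumptions that show the range:

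| Assumed instruction | Full adherence per week | Cut-off as share of full adherence |
|---|---|---|
| Once daily | 1 × 7 = 7 | 10/7 = 143% (cannot be met) |
| Twice daily | 2 × 7 = 14 | 10/14 = 71% |
| Three times daily | 3 × 7 = 21 | 10/21 = 48% |

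The same rule is impossible, moderate or lenient depending on advice the protocol does not fix.

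**3. Does the averaging period matter?** Inputs: 14 applications per week during RT (section 9.5, at its minimum), 4 to 6 weeks of RT, and 4 weeks of follow-up (synopsis). Mean over the whole span = 14 × RT weeks / (RT weeks + 4).

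| RT weeks | Mean over RT weeks | Mean over RT + 4 weeks |
|---|---|---|
| 4 | 14.0 | 56/8 = 7.0 |
| 5 | 14.0 | 70/9 = 7.8 |
| 6 | 14.0 | 84/10 = 8.4 |

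The last column lies wholly below 10. Longer follow-up lowers it further; 4 weeks of RT with the 8-week limit in section 6.1 gives 56/12 = 4.7. This result needs two conditions together: application stops at the end of RT, and the denominator runs past it. If application continued twice daily throughout, the mean would be 14 on either denominator.

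**4. Does the frequency wording matter?** Twice daily gives 14 per week, and at least twice daily gives 14 or more. Both exceed 10, so a subject who follows either text is compliant over her application period.

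**The case against.** The strongest reply is that the averaging period can be read from the text. Section 9.5 is the only place that states when KeraStat is applied, and it says during RT. Section 11.1 ties application reporting to the weekly visit, and weekly visits run only through RT. Cream is handed out at Visit 1 and the weekly visits (6.5.1, 6.5.2), and the close-out visit (6.5.3) mentions no supply. In the synopsis paragraph on the diary, treatment elsewhere means radiation, so the post-RT phrase may simply mean the time after RT. This largely stands. A reader might infer that the plan sets two conflicting durations, or that it will score perfect users at 7.0 to 8.4. The documents do not support either: no section prescribes the longer denominator. What remains is that the period is implied and not stated, while the post-RT diary and the Duration of Treatment entry leave room for another reading.

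It can also be said that the physician selects the product and the synopsis only describes how to apply it. That reconciles the choice of product, but not the frequency: sections 6.5.1 and 6.5.2 hand the instructions themselves to the oncologist.

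Finally, section 5.1 frames primary feasibility around use of KeraStat, which makes the control rate secondary to that aim. This is fair, but the synopsis and section 12.2 still promise an interval in each group.

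**Conclusion.** The control regimen is contradictory in the current text, and the control compliance rate is therefore not tied to any one assigned regimen. Its size cannot be fixed from the documents, because the physicians' instructions are not given. Under the assumed once-daily instruction, every fully adherent control would score 7 and be classed non-compliant. For KeraStat, the averaging period needs to be written down. The fall from 14 to between 7.0 and 8.4 is conditional on a denominator that the plan does not set.

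A reader might go further and conclude that the treatment contrast and the compliance rates cannot be interpreted. That does not follow. Randomization still supports a comparison of KeraStat with the control care actually delivered; what is unclear is which comparator that is. The KeraStat rate is interpretable over the RT weeks. The two KeraStat frequency wordings move nobody across the cut-off, and tubes used can be counted under either. The margin of error and the power are unchanged. This is an inconsistency to correct before analysis, not a flaw in having chosen physician-directed care as a comparator.

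**What to change.** 1. The sponsor and investigator reconcile the synopsis (Study Assessments, Test Product(s), Duration of Treatment) with sections 6.1, 6.4, 6.5.1, 6.5.2 and 9.5, so that each arm has one stated regimen and one application period. Which regimen is right is for them; no view is taken here. The two KeraStat frequency wordings should be aligned in the same pass.
2. Sections 11.1 and 12.1 state that the weekly average is taken over that application period only.
3. Section 12.1 applies the cut-off of 10 only to an arm whose assigned regimen it fits. Otherwise control is scored against the instructions given, or control applications are reported descriptively without a compliance class. The per-group interval in the synopsis and section 12.2 is edited to match.
4. One CRF field records the control product and the instructions given, so that the comparator can be described in the report.

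The cost is protocol wording and one CRF field, with the IRB approval that section 14.2 requires for an amendment. There is no change to the number of subjects, the visits or the tests.

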3. LIST OF ABBREVIATIONS AND DEFINITIONS OF TERMS

The following abbreviations and specialist terms are used in this study protocol.

Table 1: Abbreviations and Specialist Terms

Abbreviation or Specialist Term	Explanation
AE	Adverse Event
CRF	Case Report Form
CRO	Clinical Research Organization
cGMP	Current Good Manufacturing Practice
FDA	Food and Drug Administration
GCP	Good Clinical Practice
ICF	Informed Consent Form
ICH	International Conference on Harmonization
IEC	Institutional Ethics Committee
IRB	Institutional Review Board
ISO	International Organization for Standardization
KRNT	KeraNetics
SAE	Serious Adverse Event
RD	Radiation Dermatitis
SOPs	Standard Operating Procedures
SAP	Statistical Analysis Plan
USP	United States Pharmacopoeia

KeraNetics, LLC. CONFIDENTIAL Page 11

Version: 00

Effective Date:

03-01-2018

4. INTRODUCTION

4.1. Background

Radiotherapy (RT) is an effective intervention for treating breast cancer. The primary mechanism of action of RT is to create enough DNA damage within each tumor cell to prevent replication and ultimately induce programmed cell death. This mechanism extends beyond the targeted tumor to normal surrounding tissue. This field effect can be visualized by the effect of RT on the skin within a treatment portal. Approximately 85% of patients undergoing RT experience a moderate-to-severe skin reaction¹. The disturbance of the cutaneous barrier function can significantly impact both health-related quality of life and the course of treatment². If the skin reaction is severe enough, a treatment break may be recommended³. Managing the symptoms associated with skin reactions is important for ensuring completion of RT in a timely manner and increasing patient self-esteem². Current skin care recommendations typically include the use of non-fragrant, hypo-allergenic moisturizers².

KeraStat Cream is a non-sterile, non-implantable, emulsion-based wound dressing intended to act as a protective covering in the management of a variety of minor skin wounds and first and second degree (partial thickness) burns as well as skin undergoing radiation treatment. KeraStat Cream uses human hair-derived keratin proteins and is applied topically to the wound surface to absorb exudate, provide a moist environment, and create an environmental barrier supportive of healing.

All ingredients have been used in FDA-approved products. A biological safety profile has been established for the keratin protein ingredient in KeraStat Cream. Biocompatibility studies were chosen and performed in accordance with ISO 10993-1:2007, "Biological Evaluation of Medical Devices Part 1: Evaluation and Testing." This testing included a full toxicological risk assessment per ISO 10993-17 and 10993-18. Additionally, an FDA-approved hydrogel wound dressing containing the keratin proteins, water, and a preservative, called KeraStat Gel, has been subjected to a human subject Repeat Insult Patch Test (RIPT) to evaluate the irritation/sensitization potential of the product when applied to uncompromised skin. No adverse skin reactions were observed in 50 subjects evaluated in the RIPT study, and KeraStat Gel was considered a non-primary irritant and non-primary sensitizer to the skin. In addition to uncompromised skin, KeraStat Gel was tested in compromised skin to assess human sensitization study, the Skin Prick Test (SPT). The results of the SPT demonstrated that there was no humoral immune response to keratin and supported pre-clinical testing, which determined that the product would not elicit an immune response.

The current study is considered a nonsignificant risk (NSR) device study according to Food and Drug Administration (FDA) guidance and does not require an Investigational Device Exemption (IDE) in advance of study conduct. NSR device studies must follow the abbreviated requirements presented in 21 CFR 812.2(b) related to labeling, Institutional Review Board (IRB) approval, informed consent, monitoring, records, reports, and prohibition against promotion.

